## **Protocol Synopsis**

Study Title	Consumer Responses to Alcohol Warnings
Funder	NA
Clinical Phase	NA
Study Rationale	

• Policymakers and public health organizations are increasingly interested in communicating alcohol's harms to the public, including through mandated warning labels as well as mass media campaigns.

• Communicating alcohol's harms could increase consumer understanding of these harms and reduce alcohol consumption and alcohol-related health harms.

• Alcohol contributes to more than 200 health harms, giving policymakers and public health organizations many options to choose from when selecting topics to include in messages about alcohol-related harms.

• However, it remains unknown which of these topics should be prioritized in communication efforts.

Study	Primary
Objective(s)	

• To evaluate whether alcohol warnings about different topics elicit higher perceived message effectiveness than control messages.

	Secondary
	

• To evaluate whether alcohol warnings about different topics elicit higher reactance than control messages.

Study Design	Randomized experiment.
Subject	Inclusion Criteria
Population	

1. Age 21 and older

key criteria for	

2. Reside in the United States

Inclusion and	

3. Able to complete a survey in English

Exclusion:	Exclusion Criteria
	

1. Under the age of 21

2. Reside outside of the United States

3. Unable to complete a survey in English

Number of Subjects	2,500
Study Duration	Each subject's participation will last approximately 10 minutes. The enrollment period is expected to last ~1-2 weeks.

---

Study Phases	There are two phases: (1) Screening : screening for eligibility and obtaining consent and (2) Intervention : study intervention/experimental treatment.
Efficacy Evaluations	The primary outcome is perceived message effectiveness for discouraging alcohol consumption. It is measured with 1 item adapted from prior studies.
Statistical and Analytic Plan	
Primary outcome
 

• We will use linear mixed models to examine the effect of each alcohol warning topic on perceived message effectiveness compared to control topics.

 
Secondary outcomes
 

• We will use linear mixed models to examine the effect of each alcohol warning topic on message reactance compared to control topics.

Data and Safety Monitoring Plan	

• The principal investigator is responsible for data quality management and ongoing assessment of safety.

---

## **Introduction**

The goal of the analysis described here is to use data we collected through an online randomized experiment to examine consumer responses to alcohol warning messages about different topics. This analysis examines the effects of warning topic (e.g., mouth cancer, liver damage) on perceived message effectiveness (primary outcome) and message reactance (secondary outcome).

This analysis plan pre-specifies the analyses before collecting data and therefore serves as our ex-ante planned analysis.

## **Study Protocol**

Participants will complete an online randomized experiment programmed in Qualtrics. After providing informed consent, participants will view and rate messages on perceived message effectiveness (primary outcome) and message reactance (secondary outcome). Participants will be randomly assigned to 1 of 4 topic sets. Each topic set includes messages about 6 different topics: 5 warning topics and 1 control topic. (The warning topics vary across topic sets, but the control topic is the same across all topic sets). Participants will view messages about these topics in random order. Participants will view and rate 2 messages per topic (shown in random order within topic), for a total of 12 messages.

## **Statistical Considerations**

### **General Principles**

We will use a two-sided critical alpha of 0.05 to conduct all statistical tests. All confidence intervals presented will be 95% and two-sided. Analyses of the primary and secondary outcomes will include all randomized participants according to experimental conditions they were randomized to (i.e., intent-to-treat). We will use complete case analysis to handle any missing data in analyses of the primary and secondary outcomes.

### **Primary Outcome**

The primary outcome is perceived message effectiveness for discouraging alcohol consumption. We will measure perceived message effectiveness with 1 item adapted from prior studies: “How much does this message discourage you from wanting to drink alcohol?” Response options will range from not at all (1) to a great deal (5).

*Hypothesis 1.* We hypothesize that all alcohol warning topics receive higher perceived message effectiveness ratings than the control topic.

### **Secondary Outcome**

The secondary outcome is message reactance. We will measure message reactance with 1 item adapted from prior studies: “This message exaggerates the health effects of alcohol.” Response options will range from strongly disagree (1) to strongly agree (5).

*Hypothesis 2.* We hypothesize that all alcohol warning topics receive higher message reactance ratings than the control topic.

## **Statistical Methods**

1. Analyses of the primary outcome:

- a. We will use linear mixed models to **evaluate the effect of each alcohol warning topic compared to the control topic on the primary outcome of perceived message effectiveness**. We will regress perceived message effectiveness on a set of indicator variables representing each alcohol warning topic (e.g., mouth cancer, throat cancer, breast cancer, etc.), excluding the control topic as the referent. We will treat the intercept as random to account for repeated measures within participants. The coefficients on the alcohol warning topics give the average difference in mean perceived message effectiveness between each warning topic and the control topic. Hypothesis 1 will be supported if all coefficients on the alcohol warning topics are positive and statistically significant. Given the exploratory nature of the study, we do not plan to adjust p-values for multiple comparisons.
- b. In addition to testing Hypothesis 1, we will also **descriptively rank the alcohol warning topics** on the primary outcome of perceived message effectiveness. We will estimate mean perceived message effectiveness for each alcohol warning topic (averaging across messages for each topic) and rank those means.
- c. Finally, we will **descriptively rank the alcohol warning messages** on the primary outcome of perceived message effectiveness. We will estimate means for each alcohol warning message and rank those means.

2. Analyses of the secondary outcome:

- a. We will use linear mixed models to **evaluate the effect of each alcohol warning topic compared to the control topic on the secondary outcome of message reactance**. We will use the same approach as for the primary outcome (see no. 1 above).
- b. We will **descriptively rank the alcohol warning topics** on the secondary outcome of message reactance. We will estimate mean reactance for each alcohol warning topic (averaging across messages for each topic) and rank those means.
- c. We will **descriptively rank the alcohol warning messages** on the secondary outcome of message reactance. We will estimate mean reactance for each alcohol warning message and rank those means.

We do not plan to conduct moderation analyses.

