### Sample Size and Power

We plan to collect data from ~2,500 participants (~625 per topic set). We used G\*Power to estimate sample size needs. We estimated power to detect an effect of each warning topic vs. the control topic assuming an alpha=0.05 and correlation among repeated measures of 0.6 (based on a prior study of alcohol warnings). We estimated power assuming 2 repeated measures, reflecting that our contrast of interest has two within-subjects levels (warning topic vs. control).

Under these assumptions, our sample size will yield 80% power to detect a small standardized effect of Cohen's  $f=.05$  (or Cohen's  $d=.10$ ) or larger of each warning topic vs. the control topic. A prior study of alcohol warning topics found effects of this size or larger when comparing perceived message effectiveness of alcohol warning topics vs. control topics.

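### A participant random intercept alone may give per-topic standard errors that are too small or too large; participant-clustered standard errors are a cheap safeguard (minor)

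*Combined protocol and SAP*

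**What the plan says.** The Study Protocol section sets out a nested layout: "Participants will view and rate 2 messages per topic (shown in random order within topic), for a total of 12 messages". Each of the four topic sets has five warning topics of its own and one control topic shared by all sets.

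Statistical Methods 1a regresses the rating on topic indicators, with control as the reference, and adds: "We will treat the intercept as random to account for repeated measures within participants". Item 2a uses the same approach for reactance. Hypothesis 1 is supported only if every warning coefficient is positive and significant, with no multiplicity adjustment. General Principles adds "We will use a two-sided critical alpha of 0.05 to conduct all statistical tests" and "All confidence intervals presented will be 95% and two-sided".

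Two other places bear on the point. Item 1c treats messages as separate objects: "We will estimate means for each alcohol warning message and rank those means". Sample Size and Power gives one dependence figure, a "correlation among repeated measures of 0.6", applied to a two-level comparison of warning with control.

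No section includes a message term, a participant-by-topic term, a random slope, topic-specific variances or robust standard errors. None states what a data row is. One row per rating is the natural reading of 1a. The averaging over messages in 1b and the two-level power calculation also fit topic-level scores.

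**The concern.** A random intercept makes every pair of a person's ratings equally correlated and gives all topics one residual variance. The design gives reasons to doubt this on rating rows:

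- Two ratings of the same topic may agree more closely than ratings of different topics. The model then counts the second rating as more independent information than it is, and the reported standard error is too small.
- The two messages on a topic may differ in mean. With no message term, that fixed difference goes into the residual, and the reported standard error is too large.
- The outcome is a single 5-point item, so its variance may differ between topics. That can push individual topics either way.

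At stake are the individual per-topic p-values and confidence intervals. They are the primary analysis, and they are what a reader would use to decide which topics to prioritise.

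**Working it through.** **The plan's own power figure.** With f = 0.05, n = 625, 2 measures and correlation 0.6, the noncentrality is 0.05² × 625 × 2 / (1 − 0.6) = 7.81 on 1 and 624 df, which gives 79.7% power. The paired normal formula, with SD of the difference √(2 × 0.4), gives 79.8%. The stated 80% is reproduced.

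**Inputs for the standard-error check.** From the documents: 4 sets of about 625, 12 ratings per person (2 on each of 6 topics), control shared by all sets, correlation 0.6, two-sided 0.05. Assumed: 20 distinct warning topics, rating SD 1, and 0.6 as the correlation between different topics. The same-topic correlation r, the message difference D and the control-warning correlation are varied as ranges; the documents do not give them.

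**What the model fits.** Twelve ratings form 66 pairs, 6 same-topic and 60 different-topic. The fitted residual variance is

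w = 1 − (6r + 60 × 0.6)/66 + 12 × (D/2)²/11.

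- r = 0.60, D = 0: w = 0.400
- r = 0.70, D = 0: w = 0.391
- r = 0.80, D = 0: w = 0.382
- r = 0.60, D = 0.4: w = 0.444

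**What drives the true variance.** The mean of a topic's two ratings has true within-person variance (1 + r)/2 − 0.6, which is 0.20, 0.25 and 0.30 at r = 0.60, 0.70 and 0.80. The model uses w/2, which is 0.200, 0.195 and 0.191 with D = 0. As a hand check, √(0.25/0.195) = 1.13 and √(0.30/0.191) = 1.25. With D = 0.4 and r = 0.60, √(0.20/0.222) = 0.95.

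**Full calculation.** This compares the model-based variance of the random-intercept estimator with its true variance in the documented layout. Per-test error is 2 × [1 − Φ(1.96 / ratio)], where ratio is true SE over reported SE.

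| Rating rows | Reported SE | True SE | Ratio | Per-test error |
|---|---|---|---|---|
| r = 0.60, D = 0 | 0.0241 | 0.0241 | 1.00 | 5.0% |
| r = 0.70, D = 0 | 0.0238 | 0.0267 | 1.12 | 8.0% |
| r = 0.80, D = 0 | 0.0236 | 0.0292 | 1.24 | 11.3% |
| r = 0.60, D = 0.4 | 0.0253 | 0.0241 | 0.95 | 4.0% |
| r = 0.70, D = 0.4 | 0.0250 | 0.0267 | 1.07 | 6.6% |

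Unequal variance alone also matters. If control and one topic have residual variance 0.2 while other topics have 0.4 to 0.7, that topic has reported SE 0.0241 against true SE 0.0177, an error of 0.8%.

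**Topic-mean rows.** All the cases in the table give 5.0%, because averaging absorbs both the same-topic correlation and the message difference. A lower control-warning correlation is not absorbed. At r = 0.70, a value of 0.5 gives 0.0282 reported against 0.0309 true (7.4%), and 0.4 gives 0.0295 against 0.0343 (9.2%).

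**Clustered standard errors.** In simulations with a full REML fit on rating rows (4,000 data sets per case, ten cases), model-based error followed the calculated values. Participant-clustered error was 4.9% to 5.1% throughout.

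**Power with clustering**, Φ(0.10/SE − 1.96), with d in rating SDs:

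- Control-warning 0.6: 96% at r = 0.70 (SE 0.0267) and 93% at r = 0.80 (SE 0.0292).
- Control-warning 0.4: 82% at r = 0.70 (SE 0.0348) and 78% at r = 0.80 (SE 0.0367).

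**The all-significant rule.** The worst case for false support is one null topic with all others clearly positive. False support is then half the two-sided error: 8.0%/2 = 4.0% at r = 0.70 and 11.3%/2 = 5.6% at r = 0.80 (D = 0), against 2.5%.

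**The case against.** The plan is internally consistent. A random intercept implies a single within-person correlation, and the power section assumes a single correlation. If that holds for all ratings, with equal variances and equal message means, the planned standard errors are exactly right. Every departure in the table uses values that the documents do not give. The source of the 0.6 is not available here, so one cannot tell whether it describes same-topic ratings, different-topic ratings or topic means. If the analysts average to one score per topic, the headline cases vanish. The plan calls the study exploratory, and a random intercept is a common specification for repeated ratings.

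Most of this stands, and it is why the point is conditional and minor. A reader might infer that the planned p-values are known to be too optimistic. The documents do not support that: the direction depends on quantities they do not report, and two departures can cancel. At same-topic correlation 0.64 with a 0.4 SD message difference the error is 5.0%.

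What does not stand is that the plan has settled the matter. A single working correlation for a two-level power contrast does not show that same-topic and different-topic ratings are equally correlated, and 1c allows for messages that differ. Topic-mean rows are not a full answer either, since a lower control-warning correlation still gives about 7% to 9%.

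**Conclusion.** The point holds as a minor, cheap improvement. If 1a and 2a are fitted to individual ratings, the per-topic standard errors may be too small or too large, and the plan has no safeguard in either direction. The range shown runs from about 4% per-test error (equal correlations, 0.4 SD message difference) to about 11% (same-topic correlation 0.80, equal message means). Unequal topic variances or a lower control-warning correlation can take it outside that range. All of this rests on the assumptions listed, and only the 0.6 comes from the plan.

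Two further inferences should be resisted. The stated 80% power is not overturned: the planned model uses two ratings per topic and control ratings from all sets, so power at d=0.10 with clustered errors is near or above 80% in the cases tried. Nor are the Hypothesis 1 and 2 decisions undermined, because requiring every coefficient to be significant leaves the rule little affected. Clustering leaves the coefficients and rankings as they are.

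**What to change.** Add to Statistical Methods 1a, and by reference 2a: *The model is fitted with one row per rating (12 per participant). Standard errors, tests and 95% confidence intervals for the topic coefficients are cluster-robust, with participant as the cluster.*

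This settles the row unit and covers same-topic correlation, message differences, unequal variances and control-warning correlation without having to choose among them in advance. With about 2,500 clusters no small-sample correction is needed.

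The cost is two sentences and a standard software option, with no change to design, model or sample size. With equal message means, intervals widen by about 12% at same-topic correlation 0.70 and 24% at 0.80. They narrow by about 5% if correlations are equal and messages differ by 0.4 SD. In the harshest case tried (same-topic 0.80, control-warning 0.4), power at d=0.10 is 78%. Clustering by participant does not justify generalising from the two tested messages to all messages on a topic; that is a separate question.

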### Sample Size and Power

We plan to collect data from ~2,500 participants (~625 per topic set). We used G\*Power to estimate sample size needs. We estimated power to detect an effect of each warning topic vs. the control topic assuming an alpha=0.05 and correlation among repeated measures of 0.6 (based on a prior study of alcohol warnings). We estimated power assuming 2 repeated measures, reflecting that our contrast of interest has two within-subjects levels (warning topic vs. control).

Under these assumptions, our sample size will yield 80% power to detect a small standardized effect of Cohen's  $f=.05$  (or Cohen's  $d=.10$ ) or larger of each warning topic vs. the control topic. A prior study of alcohol warning topics found effects of this size or larger when comparing perceived message effectiveness of alcohol warning topics vs. control topics.

### **Exclusions and Outliers**

We will exclude participants who do not complete the survey or who complete the survey implausibly quickly (defined as  $<1/3$  of the median completion time).

